2.4 Study Hypothesis

The hypothesis of this study is that focal treatment with ExAblate MRgFUS has the potential to be an effective non-invasive treatment for intermediate risk, organ-confined prostate lesions, with a low incidence of morbidity. The study hypothesis will be tested by measuring treatment-related safety and effectiveness parameters in the ExAblate MRgFUS treated patients, as described above.

3 DESCRIPTION OF PATIENT POPULATION

This study involves patients with organ-confined, intermediate risk prostate lesions for treatment with the ExAblate 2100 Prostate System.

3.1 Subject Enrollment

Patients will be counseled concerning the research nature of this study, including potential risks and benefits associated with participation in the study. Patients providing written informed consent will be screened for study eligibility.

3.2 Inclusion Criteria

1. Male subjects age 50 and older.
2. Biopsy proven adenocarcinoma of the prostate (using a IMAGE-guided 14+ core mapping biopsy), and targeted cores as needed obtained up to 6 months prior to scheduled treatment.
3. Patient with intermediate risk, early-stage organ-confined prostate cancer (T1a up to T2b, N0, M0) and voluntarily chooses ExAblate thermal ablation as the non-invasive treatment, who may currently be on watchful waiting or active surveillance and not in need of imminent radical therapy.

Focal MR-Guided Focused Ultrasound Surgery of Intermediate risk, Localized Prostate Lesions

4. Patient with PSA less than or equal to 20 ng/mL
5. Gleason score r 7 (4 + 3 or 3 + 4), based on mapping prostate biopsy, with no more than 15mm cancer in maximal linear dimension in any single core.
6. Single hemilateral index Gleason 7 lesion, identified in the prostate based on biopsy mapping with supporting MRI; may have secondary Gleason 6 lesion on ipsilateral or contralateral side confirmed with biopsy and/or MRI.
7. Gleason 7 tumors must be MRI visible:
 - a. In the event that a tumor is in contact with the capsule, the length of the contact should be \leq 5 mm, on axial images.
 - b. Largest imaging dimension of cancerous finding $<$ 20-mm
8. No definite evidence of extracapsular extension or seminal invasion by MRI
9. Patient should be eligible for both spinal/epidural anesthesia (planned procedure), and general anesthesia (in case of complication, requiring intervention).
10. Patient is willing and able to give consent attend all study visits and complete all questionnaires as defined in the protocol
11. Tumor distance, including tumor free margins, should not be more than 40mm from the rectal wall.

3.3 Exclusion Criteria

- 1 ASA status $>$ 2
- 2 Contraindications to MRI
 - 2.1 Claustrophobia
 - 2.2 Implanted ferromagnetic materials or foreign objects
 - 2.3 Known intolerance to the MRI contrast agent
- 3 Severely abnormal coagulation (INR $>$ 1.5)
- 4 Patients with unstable cardiac status including:
 - 4.1 Unstable angina pectoris on medication
 - 4.2 Patients with documented myocardial infarction within 40 days prior to enrolment
 - 4.3 Congestive heart failure NYHA class IV
 - 4.4 Patients with unstable arrhythmia status, already on anti-arrhythmic drugs
- 5 Severe hypertension (diastolic BP $>$ 100 on medication)
- 6 Severe cerebrovascular disease (multiple CVA or CVA within 6 months)

Focal MR-Guided Focused Ultrasound Surgery of Intermediate risk, Localized Prostate Lesions

- 7 History of bilateral orchiectomy, PCa-specific chemotherapy, brachytherapy, cryotherapy, Photodynamic therapy or radical prostatectomy for treatment of prostate cancer; any prior radiation therapy to the pelvis for prostate cancer or any other malignancy.
- 8 Patient under medications that can affect PSA for the last 3 months prior to MRgFUS treatment (Androgen Deprivation Treatment; alpha reductase inhibitors)
- 9 Patients with lesions of Gleason 7 or greater outside the planned treatment area.
- 10 Individuals who are not able or willing to tolerate the required prolonged stationary supine position during treatment (approximately 3 hrs. sonication time)
- 11 Any rectal pathology, anomaly or previous treatment, which could change acoustic properties of rectal wall or prevent safe probe insertion (e.g., fistula, stenosis, fibrosis, inflammatory bowel disease, etc).
- 12 Any spinal pathology which can prevent safe administration of epidural/spinal anesthesia
- 13 Identified calcification of 2 mm or more in largest diameter neighboring the rectal wall (in a distance of less than 5 mm) and interfering with the acoustic beam path.
- 14 Lower limb musculoskeletal fixed deformities preventing probe insertion or patient positioning during procedure.
- 15 Prostate with multiple cystic lesions.
- 16 Evidence of distant prostate cancer, i.e., including lymph nodes and/or metastasis of cancer on imaging
- 17 Bladder cancer
- 18 Urethral stricture/bladder neck contracture
- 19 Active UTI
- 20 Prostatitis NIH categories I, II and III.
- 21 Compromised renal function
- 22 Implant near (≤ 1 cm) the prostate
- 23 Interest in future fertility
- 24 Current participation in another clinical investigation of a medical device or a drug or has participated in such a study within 30 days prior to study enrollment.

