Post-therapy changes from Baseline to 24 months will be assessed for PSA levels along with results of the patient completed FACT-P (Version 4), ICIQ-SF, IPSS, IIEF-15 and SF12 questionnaire. See Section 5 for the full schedule of events.

Biopsy mapping must be performed to localize the region of interest for the focal ExAblate treatment. The standards of performing biopsy will follow site specific mapping procedures, but the procedure must meet the minimum study guidelines for a 14 core mapping biopsy where 2 of these biopsies are directed anteriorly on the right and left hemi-gland as discussed in **Appendix C**.

2.1.1 Prostate glands should be delineated into at least 14 sectors.

Pathology results will be performed by the center's pathology group according to their standard protocol, but cores must be individually labeled by anatomical location for mapping purposes.

An ExAblate treatment's target volume/ROT (Region of Treatment) will be defined as an intra-prostatic volume containing a lesion that was identified by positive 14 core IMAGE-guided mapping biopsy where 2 of these biopsies are directed anteriorly on the right and left hemi-gland.

The goal of the ExAblate MRgFUS treatment is to completely ablate the lesion, while sparing crucial structures; i.e., rectal wall, external sphincter, bladder wall, and optionally the urethra and one or both neurovascular bundles.

Biopsy-confirmed lesions that are visible on T2w MRI will be treated based on MR visualized lesion margins with surrounding 5 mm lesion-free margins, wherever clinically applicable (i.e., treatment will not include 5 mm lesion free margins if these extend into structures to be spared (e.g., rectal wall, external urethral sphincter, bladder wall, etc.)

Focal MR-Guided Focused Ultrasound Surgery of Intermediate risk, Localized Prostate Lesions

When a single lesion extends into an adjacent sector, both sectors will be treated.

Overall treatment volume should be up to 50% of the prostate gland for prostate volume <60cc, and up to 30cc should the entire prostate volume be larger than 60cc and avoid as much as possible vulnerable structures.

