4.2 Pre-Treatment Procedures

1. Patients will be screened for eligibility for the study. Those meeting the criteria will be offered to participate and sign an informed consent form.
2. Complete medical history, physical exam with DRE and concomitant medications will be obtained to determine patients' general health status, and presence of symptoms. The following questionnaires will be completed by participating subjects: FACT-P, ICIQ-SF, IPSS, IIEF-15, and SF-12.
3. Blood tests (PSA, CBC, serum chemistries), urinalysis and CT will be performed to verify compliance with eligibility criteria.
 - a. Urinalysis will include Specific gravity, pH, Glucose, Protein, RBC, Casts, WBC, Bacteria, culture, if indicated
4. IMAGE-guided mapping prostate biopsy (TPBx or TRBx per Appendix C) followed by pathology examination and analysis will be performed to evaluate oncology staging of disease and subject's eligibility for the study.
5. Pre-treatment multi-parametric (1.5/3T) MRI scans (E-coil may be used) will be performed not less than 6 weeks after a prostate biopsy. CT will also be performed.
6. Subject will have assessment for anesthesia (general and epidural) by an attending Anesthesiologist.
7. For subjects who met all eligibility criteria and had formally agreed to participate in the study, ExAblate MRgFUS treatment will be scheduled.
8. Treatment will be performed after a minimum of 30 days from IMAGE-guided prostate mapping biopsy.
9. Subject will be instructed to adhere to low residue diet without milk ingredients 48 hours pre-treatment, with no oral intake during the last 12 hours before treatment. On the evening prior to the procedure and on the morning of the treatment, the subject will undergo colon preparation (using laxatives) similar to colonoscopy preparation. To avoid existence of any fecal residue in the rectum during the procedure, two (2) hours prior to anesthesia, a cleansing enema will be performed.

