4.4.2 Wherever possible, in cases of potential surgical resection of the gland MRgFUS-treated patients, pathology results will be evaluated and compared to the treatment and post treatment data.

5 Study Visit Schedule

See visit schedule on next pages.

**Focal MR-Guided Focused Ultrasound Surgery
of Intermediate risk, Localized Prostate Lesions**

PCa003 Study Schedule				
Visit	Window Allowance	Clinical Office and Lab Tests	Imaging **	Questionnaires
Screening	—	DRE; PSA IMAGE-guided TPBx or TRBx; Clinical labs for CBC, serum chemistries and urinalysis (cultures, if indicated); Physical Exam Concomitant medications	CT, Multi-parametric MRI (E-coil may be used)	FACT-P (v4); ICIQ-SF; IIEF-15 (SHIM); IPSS SF-12
Treatment ***	—	DRE; peripheral oxygen saturation, heart rate, and blood pressure; AEs	MR for planning, treatment and post Tx	Pre-Txt: NRS, FACT-P (v4); ICIQ-SF; IIEF-15 (SHIM); IPSS; SF-12 Post-Txt - NRS
1 week	±3 days	AEs; Physical exam; Concomitant medications		NRS; ICIQ-SF
1 month	± 7 days	AEs; Physical exam with DRE; Proctoscopy and/or post-void residual and Uroflowmetry if indicated; Concomitant medications		ICIQ-SF; IPSS NRS
3 months	± 1 week	AEs; Physical exam; DRE; Concomitant medications		FACT-P (v4); ICIQ-SF; IIEF-15 (SHIM); IPSS; SF-12;
6 months	± 1 month	AEs; Physical exam; DRE; urinalysis (culture, if indicated), PSA; TRBx or TPBx; Concomitant medications	Multi-parametric MRI	FACT-P (v4); ICIQ-SF; IIEF-15 (SHIM); IPSS; SF-12
9 months	±1 month	AEs; Physical exam; DRE; Concomitant medications		FACT-P (v4); ICIQ-SF; IIEF-15 (SHIM); IPSS ; SF-12

**Focal MR-Guided Focused Ultrasound Surgery
of Intermediate risk, Localized Prostate Lesions**

12 months	± 2 month	AEs; Physical exam; DRE; PSA Clinical labs for CBC, serum chemistries and urinalysis (cultures, if indicated); post-void residual and Uroflowmetry if indicated; Concomitant medications		FACT-P (v4); ICIQ-SF; IIEF-15 (SHIM); IPSS; SF-12
18 months	± 2 months	AEs; Physical exam; DRE, urinalysis (Culture, if indicated); PSA Concomitant medications		FACT-P (v4); ICIQ-SF; IIEF-15 (SHIM); IPSS; SF-12
24 months	± 2 months	AEs; Physical exam; DRE; PSA Clinical labs for CBC, serum chemistries and urinalysis (cultures, if indicated); post-void residual and Uroflowmetry if indicated; IMAGE-guided TRBx or TPBx; Concomitant medications		FACT-P (v4); ICIQ-SF; IIEF-15 (SHIM); IPSS ; SF-12

Focal MR-Guided Focused Ultrasound Surgery of Intermediate risk, Localized Prostate Lesions

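### The exclusion for PSA-affecting drugs is timed from treatment, but the only scheduled pre-treatment PSA is taken at screening on an unspecified date, so the 20 ng/mL check and the baseline can rest on an on-drug value

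*Combined protocol and SAP*

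**What the plan says.** All places are in the combined protocol and SAP.

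- **Drug window.** Section 3.3 item 8 excludes a "Patient under medications that can affect PSA for the last 3 months prior to MRgFUS treatment", and names androgen deprivation and alpha reductase inhibitors. The interval ends at treatment.
- **PSA limit.** Section 3.2 item 4 requires a "Patient with PSA less than or equal to 20 ng/mL". It gives neither a sampling date nor a drug-free condition.
- **Purpose of the sample.** Section 4.2 item 3: "Blood tests (PSA, CBC, serum chemistries), urinalysis and CT will be performed to verify compliance with eligibility criteria".
- **When PSA is scheduled.** The Screening row of the Section 5 visit table reads "DRE; PSA IMAGE-guided TPBx or TRBx; Clinical labs for CBC" and has a dash where the visit window would be. The Treatment row lists no blood test. The next PSA is at 6 months.
- **Use as an outcome.** Section 2.1: "Post-therapy changes from Baseline to 24 months will be assessed for PSA levels". Baseline is not defined for PSA. Section 2.3 makes PSA a secondary effectiveness measure, and Section 6.2.1 summarises it descriptively.
- **Biopsy timing, for context.** Section 3.2 item 2 covers the mapping biopsy and "targeted cores as needed obtained up to 6 months prior to scheduled treatment". Section 4.2 item 8 adds: "Treatment will be performed after a minimum of 30 days from IMAGE-guided prostate mapping biopsy". Neither limit is stated for PSA.

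**The concern.** An exclusion for drugs that alter PSA exists to protect a PSA measurement. Here it protects a day on which no PSA is taken. The sample that decides eligibility and starts the PSA comparison lies earlier, and nothing requires it to be drug-free.

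Two things are at stake. First, the two ends of the PSA comparison may be measured under different conditions: the first on or soon after a suppressing drug, the later ones long after it. The study has a single arm (Section 4.1), so no control group absorbs that artefact. Second, a man whose unsuppressed PSA is above the protocol's own limit could meet it on a lowered reading.

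**Working it through.** The plan gives no figure to reproduce here, and the sample size of 100 to 103 has no bearing on the point. The check is one of timing, followed by an illustration.

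**1. Drug-free time at the sample.** Let t be the months from the screening PSA to treatment. A man who only just meets item 8 stopped 3 months before treatment. His drug-free time at the draw is max(0, 3 − t).

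| t (months) | Minimum drug-free time at draw | On drug at draw and still compliant? |
|---|---|---|
| 1 | 2 months | no |
| 2 | 1 month | no |
| 3 | 0 | no |
| 4 | 0 | yes |
| 6 | 0 | yes |

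The clear failure is t > 3. The man can then stay on the drug for up to t − 3 months after the draw and still comply.

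**2. Can t exceed 3?** The documents set neither a minimum nor a maximum for t. The eligibility biopsy may be up to 6 months old at treatment, and PSA belongs to the same Screening visit, so t > 3 is possible. If PSA shared the biopsy window (an assumption), the exposed part would be (6 − 3)/(6 − 0.99) = 60% with the 30-day minimum. It would be (6 − 3)/(6 − 1.38) = 65% if the 6-week interval from biopsy to MRI in Section 4.2 item 5 sets the minimum. These are shares of a calendar window, not of patients.

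**3. The other end of the comparison.** The 6-month visit has a window of ±1 month. The same man, if he does not resume the drug, is then at least 3 + 5 = 8 months off it.

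**4. Illustrative size.** Let s be the proportion by which the drug lowers PSA at the draw. The documents do not give s, so a range is shown. The illustration assumes full recovery by follow-up.

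- Unsuppressed PSA behind a reading of 20 ng/mL = 20/(1 − s).
- Observed fall when the true fall is f: 1 − (1 − f)/(1 − s).

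| s (assumed) | Unsuppressed PSA at a reading of 20 | True fall of 50% appears as | True fall of 70% appears as |
|---|---|---|---|
| 10% | 20/0.90 = 22.2 | 1 − 0.5/0.90 = 44% | 1 − 0.3/0.90 = 67% |
| 25% | 20/0.75 = 26.7 | 1 − 0.5/0.75 = 33% | 1 − 0.3/0.75 = 60% |
| 50% | 20/0.50 = 40.0 | 1 − 0.5/0.50 = 0% | 1 − 0.3/0.50 = 40% |

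**5. Effect on a group summary.** Suppose 100 men and a mean percentage fall (the plan does not name the summary). With a true fall of 50%, each affected man lowers the mean by (50 − 44.4)/100 = 0.06, (50 − 33.3)/100 = 0.17 or (50 − 0)/100 = 0.5 percentage points. The total depends on how many such men there are, which the documents do not show.

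**The case against.** The strongest reply is that the problem needs several things together: a PSA drawn well before treatment, use of a listed drug at that draw, and stopping afterwards. Such men may be few. Concomitant medications are recorded at Screening (Section 4.2 item 2 and the Section 5 table), so the investigator would see the use. PSA is secondary, and the error understates the benefit. Stage, Gleason score, core length and MRI criteria in Section 3.2 also guard entry, so a low PSA alone does not admit anyone. All of this stands and limits the weight of the point. It does not close the gap, because no rule links the medication record to the PSA sample.

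A reader might infer that PSA is drawn 1 to 6 months before treatment. The documents do not say so: those limits belong to the mapping biopsy. Section 4.2 lists blood tests before the biopsy, but the list is not a dependable chronology, since CT appears in both item 3 and item 5. The draw could be close to treatment or earlier than 6 months.

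A reader might also infer that any screening PSA from a recent drug user is suppressed. For draws up to 3 months before treatment a compliant man is already off drug, and residual suppression cannot be judged from these documents.

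Finally, item 8 could be read as excluding only men on the drug throughout the 3 months. That reading is looser and would widen the gap.

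**Conclusion.** The point holds in a limited form. Item 8 is a stated rule tied to an event at which PSA is not measured. For a screening PSA drawn more than 3 months before treatment, a man can comply and still have an on-drug value used for the 20 ng/mL limit and, in all likelihood, as his baseline. For later draws his drug-free time may be under 3 months, with an unknown effect.

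This rests on one inference: that the screening value is Baseline PSA. It is the only scheduled candidate, but the plan does not say so. The suppression figures are assumptions, and the number of men affected is unknown.

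The consequence is confined to one eligibility limit and one secondary, descriptive outcome. The documents do not support a claim that the primary result is affected, because Section 6.2.1 bases it on the 6-month biopsy. Nor do they support a claim that the device is flattered, because a suppressed baseline shrinks the apparent fall. This is a cheap improvement, not a threat to the trial's main conclusion.

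**What to change.** **In the analysis, for all patients including the 81 already treated by 20 September 2018 (Sections 2.1.2 and 6.1):**

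- State which sample is Baseline PSA, and list its date relative to treatment.
- From the concomitant-medication record, flag every Baseline PSA drawn while a drug named in item 8 was in use, or within the protocol's own 3-month interval after it was stopped. The plan does not spell out that stop dates are captured. Where one is missing, say so and treat the man's status as unknown.
- Report PSA change with and without flagged men, and give the number flagged.

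**For patients still to be treated** (100 − 81 = 19 to 103 − 81 = 22 as of that date): reconcile Section 3.2 item 4, Section 3.3 item 8, Section 4.2 item 3 and the Section 5 table, so that the exclusion window and the PSA used for eligibility and Baseline refer to the same time point. How that is done, and what interval applies, is for the sponsor to decide.

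The analytic part costs one definition, one flag and one sensitivity listing.

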4 INVESTIGATION PLAN

4.1 Study Design

This is a multi-center, prospective, single arm study to evaluate MRgFUS treatment of intermediate risk, organ-confined prostate lesions. All subjects will be treated and then followed up clinically for up to 24 months to evaluate any procedure or device related

**Focal MR-Guided Focused Ultrasound Surgery
of Intermediate risk, Localized Prostate Lesions**

adverse events as well as to assess efficacy endpoints of the study. Additional data related to quality of life of treated subjects will also be collected.

4.2 Pre-Treatment Procedures

1. Patients will be screened for eligibility for the study. Those meeting the criteria will be offered to participate and sign an informed consent form.
2. Complete medical history, physical exam with DRE and concomitant medications will be obtained to determine patients' general health status, and presence of symptoms. The following questionnaires will be completed by participating subjects: FACT-P, ICIQ-SF, IPSS, IIEF-15, and SF-12.
3. Blood tests (PSA, CBC, serum chemistries), urinalysis and CT will be performed to verify compliance with eligibility criteria.
 - a. Urinalysis will include Specific gravity, pH, Glucose, Protein, RBC, Casts, WBC, Bacteria, culture, if indicated
4. IMAGE-guided mapping prostate biopsy (TPBx or TRBx per Appendix C) followed by pathology examination and analysis will be performed to evaluate oncology staging of disease and subject's eligibility for the study.
5. Pre-treatment multi-parametric (1.5/3T) MRI scans (E-coil may be used) will be performed not less than 6 weeks after a prostate biopsy. CT will also be performed.
6. Subject will have assessment for anesthesia (general and epidural) by an attending Anesthesiologist.
7. For subjects who met all eligibility criteria and had formally agreed to participate in the study, ExAblate MRgFUS treatment will be scheduled.
8. Treatment will be performed after a minimum of 30 days from IMAGE-guided prostate mapping biopsy.
9. Subject will be instructed to adhere to low residue diet without milk ingredients 48 hours pre-treatment, with no oral intake during the last 12 hours before treatment. On the evening prior to the procedure and on the morning of the treatment, the subject will undergo colon preparation (using laxatives) similar to colonoscopy preparation. To avoid existence of any fecal residue in the rectum during the procedure, two (2) hours prior to anesthesia, a cleansing enema will be performed.

4.3 Treatment Procedures

On day of treatment before any procedures, patient should complete the NRS, ICIQ-SF, FACT-P, IPSS, IIEF-15, and SF-12 questionnaires before prepping for treatment.

1. IV line will be inserted.

Focal MR-Guided Focused Ultrasound Surgery of Intermediate risk, Localized Prostate Lesions

2. The recommended anesthesia for the treatment is either epidural or general. Anesthesia should allow continuous pelvic muscle relaxation without any movement throughout the procedure. Analgesics may be administered prior to and during the procedure.
3. Bladder drainage: The procedure requires continuous bladder drainage during treatment including planning and post-treatment imaging scans. A Foley catheter would usually be adequate for continuous bladder drainage unless the urethra is included in treatment area; where a suprapubic catheter will be used for urine drainage, per site standards.
4. Prophylactic antibiotics will be administered prior to procedure, in accordance with local standard of care.
5. The system will be prepared for the treatment according to instructions provided in the Operator Manual. Specifically, the endorectal balloon covering the FUS transducer will be prepared by partial filling it with degassed water prior to the patient's arrival; lack of air bubbles in the balloon will be confirmed by the operator. Degassed water temperature inside the rectal balloon during its insertion should be not under ~34°C to avoid anal spasm while inserting the endorectal probe.
6. At this stage subject will be inserted into the MRI-ExAblate suite.
7. Subject will be placed on the treatment table in Head First, supine position with bent knees and slightly elevated legs on the MRgFUS treatment table.
8. Vital signs (i.e., peripheral oxygen saturation, heart rate, and preferably blood pressure) will be monitored throughout entire procedure using MR compatible equipment. Other measurements for applied anesthesia will be based on the decision of the attending Anesthesiologist.
9. Attending physician will perform a rectal examination.
10. After lubricating the probe with non-viscous water-based ultrasound-transparent-gel and carefully filling the patient's rectum with about 10cc of gel (using a large opening syringe to avoid air bubbles formation) the endorectal probe will be inserted through the patient's anus while the patient is in supine position with his knees bent. (Screening imaging may provide some general information regarding expected probe's location, based on specific anatomy).
11. Once inserted and reasonably positioned, the probe will be locked to the positioner system. Additional water will be pumped into the balloon. The balloon should be inflated to achieve tight contact with the entire circumference of the rectal wall; thus, achieving adequate coupling and avoiding air bubbles to enter between the endorectal balloon and the rectal wall.
12. An MRI localizer will be performed to verify positioning of the probe with relation to the prostate and the treatment area. If positioning corrections will be required, they will be done with repeated localizer imaging.

Focal MR-Guided Focused Ultrasound Surgery of Intermediate risk, Localized Prostate Lesions

13. High quality T2w images, and other MR protocols, if clinically beneficial, will be acquired for planning.
14. T1w Axial images will be acquired in order to verify acoustic coupling between the rectum and the cooling balloon.
15. Water temperature in the rectal cooling balloon would be set to 37°C to produce baseline reference for thermometry. Following acquisition of this baseline thermometry, ExAblate system would start circulation of cold degassed water in the balloon, providing sufficient protection of the rectal wall.
16. Meanwhile, treating physician will draw the prostate capsule; the capsule will be further used for motion detection and for treatment planning by the WS.
17. The treating physician will identify the focus/foci or positive sector(s) to be targeted on the current scan and draw the desired ROT (Region of Treatment) using MR images on one scan orientation (preferably, axial view), and verify the ROT(s) on the two other orientations (sagittal and coronal views). In case of clearly visible lesion boundaries on T2w-MRI, the ROT will be drawn to include the entire focus with surrounding 5mm of lesion free tissue margins where applicable (lesion free margins will not be kept if they include the rectal wall or the sphincter, for example). Whenever biopsy confirmed lesion boundaries are not clearly visible on T2-w MRI, the physician will draw the selected sector(s) based on positive core(s) coordinates. In patients with a single biopsy proven focus, when an additional (second) focus which, based on multi-functional MRI, is also in need of treatment based on multi-functional MRI is found, but has not been confirmed by biopsy, the investigator may treat both the biopsy proven focus and the MRI suspicious focus, providing total ablated volume does not exceed 15mm plus 5mm lesion free margins for each lesion. Overall treatment volume should be up to 50% of the prostate gland for prostate volume <60cc, and up to 30cc should the entire prostate volume be larger than 60cc. (Please note: in case an MRI suspicious focus is found in addition to two biopsy confirmed foci – the patient will be excluded from the study).
18. Treating physician will also mark the following safety regions that should be spared (i.e., rectal wall, urethral sphincters and bladder wall; urethra and NVB's preservation will be per clinical decision)
19. A central location of the ROT will be sonicated using low thermal dose, generating sub-lethal sonication, to reconfirm targeting geometrical accuracy in the patient.
20. Continuing with treatment process, acoustic energy transmission at therapeutic power level, accompanied with thermometry, will be performed to verify that thermal dose correlates well with the system's predicted dose. Energy levels will be adjusted as necessary to achieve sufficient level of heating to allow tissue coagulation.

Focal MR-Guided Focused Ultrasound Surgery of Intermediate risk, Localized Prostate Lesions

- 21.** Actual treatment will begin. Per each slice, planning software will compute the treatment plan with the beam path delineated. Treating physician will review/edit the sonications and make modifications as needed. Sonications will be performed according to plan.
- 22.** Effect of each sonication will be measured by MR thermometry. Acoustic power will be adjusted throughout the treatment, to achieve temperatures between 65°C and 85°C at focal point.
- 23.** Sonications will continue until entire target volume has been treated. The goal is a total procedure (i.e. ablation or sonication) time of up to 180 minutes. If the doctor determines the planned treatment is not possible after the first 3 therapeutic sonications, and another treatment session is not planned, the patient will be considered a screen failure and exited from the study. The reason for early exit will be documented on the CRF. The patient will be taken to recovery area for observation and release. The patient will undergo a 1-week follow-up visit for safety purposes, prior to study exit.
- 24.** After completion of the treatment, a final MR scan will be done. This scan will include T2 weighted and T1 contrast enhanced sequences including subtraction to evaluate tissue ablation.
- 25.** Transrectal device will be removed by physician and then patient will be transferred from the magnet/ ExAblate Suite to a recovery room for an observation period, according to clinical considerations.
- 26.** Treatment exports and all MR images taken during the study will be archived by the Sponsor.
- 27.** In the event of an incomplete treatment due to device failure, patient request, physician's decision, or unforeseen circumstance, a second treatment will be offered to the patient, provided no medical contraindications exist. Second treatment will be scheduled within 12 weeks from the original treatment. Patient follow-up visits will be based on the date of the second treatment.
- 28.** Patient should complete a post-treatment NRS.

Focal MR-Guided Focused Ultrasound Surgery of Intermediate risk, Localized Prostate Lesions

